## Coding systems utilized

The original database uses the following variables which are of interest for the data analysis. In the following list, unless otherwise noted, x represents the moment of measurement (1=baseline, 4=last visit at 90 days after treatment). Note that for Barthel Index and modified Rankin Scale, only scores at visits 2, 3, and 4 (30, 60 and 90 days after baseline, respectively) are available, with no value at baseline.

- RDMNUM = randomization number (unique to each participant)
- 
- Western Aphasia Battery
  - WABAQ\_x = Aphasia Quotient (0-100%)
- NIH Stroke Scale (Score)
  - NIHSST\_x = total score (0-42)
- Barthel Index
  - BIT\_x = total score (0-100)
- Modified Rankin Scale

- MRS\_x = total score (0-6 where 0=no symptom and 6=dead)

AEs and SAEs were stored in a separate database, from which we will retrieve the following information:

- Randomization number
- Whether the AE represents a SAE or not
- Based on the nature of the AE, some will be further classified by a clinician as being of the following nature:
  - Neurological
  - Psychiatric
  - Cardiovascular
  - Renal
  - Hematological
  - Gastrointestinal
  - Metabolic
  - Respiratory
  - Immune-related
  - ENT
  - Ophthalmic

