## Study objectives

### Primary objectives

The primary objective of the ESCAS study is to assess the efficacy of Cerebrolysin and speech therapy versus placebo (saline solution) and speech therapy at 30, 60, and 90 days after baseline. Efficacy will be evaluated using the Western Aphasia Battery (Romanian translated version) scores at each time point. The primary outcome measure is the change in Western Aphasia Battery score from baseline to each follow-up time point (30, 60, and 90 days).

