## Comparability between study groups

Compatibility between groups will be tested for the following variables: age (at stroke onset), gender, education level, writing hand, alcohol and other substance abuse, WAB scores (and their specific subscales) and NIHSS scores.

- Dichotomous variables will be tested using Chi test or, where its assumptions are not met due to small group size, Fisher's exact test.
- Qualitative ordinal variables, such as education level or alcohol/substance abuse, will be tested using Wilcoxon rank-sum tests.
- For quantitative variables, initially, normality distribution will be assessed for each group individually using the Shapiro-Wilk test. If the values for at least one group are not normally distributed, Wilcoxon rank-sum tests will be used. If values from both groups are normally distributed, equality of variances will be assessed using Bartlett test and then a Student T test for unpaired samples and equal or unequal variances will be used.

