## Exploratory statistics

For WAB scores (and their specific subscales) as well as for NIHSS scores, we will calculate the differences between the scores at visits 2/3/4, and their corresponding baseline scores. These differences will be denoted with a lowercase letter "d." Throughout this section, we will refer to these values as *differentials*.

We will assess the normality of the differentials distributions for each group and visit using the Shapiro-Wilk test.

- If the distributions of the differentials show no statistically significant differences compared to the normal distribution, across all groups and visits, then those differentials will be tested against null hypotheses of  $\mu=0$  using one sample Student T test. This would be the equivalent of testing the values of the scores for each group, at visit 2/3/4, against the baseline measurements of each respective group using paired-sample Student T test. Moreover, for each visit, we will compare the differentials between groups using Student T test for unpaired samples and equal or unequal variances, depending on the result of a Bartlett test for variance equality between groups.
- In cases where significant differences exist in the distribution of the differential values for certain groups and visits, compared to the normal distribution, we will test all differentials against the null hypothesis of location=0 using a one-sample Wilcoxon signed-rank test. This approach is equivalent to comparing the values of the scores for each group at visits 2, 3, and 4 against their corresponding baseline measurements using a Wilcoxon signed-rank test. Moreover, for each visit, we will compare the differentials between groups using a Wilcoxon rank-sum test.

For BI and mRS scores, differences from visit 2 to visit 3 and 4 respectively will be assessed in the same way, with paired-sample tests, and differences between groups will be assessed using unpaired-samples tests. .

The number of patients with at least an active AE, SAE and specific AE class, will be reported. Incidence of AEs, SAEs and AE specific classes will be compared between groups using

Chi test or where its assumptions are violated, Fisher's exact test. Moreover, the number of AEs and SAEs for each patient will be compared between groups using Wilcoxon rank-sum tests.

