# Some general functions ----
beautiful.p.value<-function(x){ #beautiful p value, if strictly under 0.001 print as <0.001,
otherwise print as =0.***
  x<-as.numeric(x)
  if(is.na(x))
    return("NA")
```

```
if(is.nan(x))
  return("NaN")
if(x<0.001)
  return("<0.001")
return(paste("",round(x,3),sep=""))
}
test.numeric.unpaired<-function(t1,t2){
  ret<-list()
  ret$sum_nas<-sum(is.na(t1))+sum(is.na(t2))
  t1<-t1[!is.na(t1)]
  t2<-t2[!is.na(t2)]
  if(length(unique(t1))==1)
    ret$shapiro.p.t1<-1
  else
    ret$shapiro.p.t1<-shapiro.test(t1)$p.value
  if(length(unique(t2))==1)
    ret$shapiro.p.t2<-1
  else
    ret$shapiro.p.t2<-shapiro.test(t2)$p.value
  if(ret$shapiro.p.t1<0.05|ret$shapiro.p.t2<0.05){ # if any of them is not normally distributed
    ret$final.test<-"Wilcoxon rank sum"
    ret$p.value<-wilcox.test(t1,t2,paired = F)$p.value
  }else{
    ret$bartlett.p<-bartlett.test(list(t1,t2))$p.value
    if(ret$bartlett.p<0.05){ # unequal distrib
      ret$final.test<-"Student T test for unpaired samples and unequal variances"
      ret$p.value<-t.test(t1,t2,paired = F,var.equal = F)$p.value
    }else{
      ret$final.test<-"Student T test for unpaired samples and equal variances"
      ret$p.value<-t.test(t1,t2,paired = F,var.equal = T)$p.value
    }
  }
  return(ret)
}
test.numeric.paired.2<-function(t1,t2){
  ret<-list()
  if(length(t1)!=length(t2))
    stop("Different lengths!")
  ret$na_vals<-is.na(t1)|is.na(t2)
  t1<-t1[!ret$na_vals]
  t2<-t2[!ret$na_vals]
  ret$shapiro.p.t1<-shapiro.test(t1)$p.value
  ret$shapiro.p.t2<-shapiro.test(t2)$p.value
  if(ret$shapiro.p.t1<0.05|ret$shapiro.p.t2<0.05){ # if any of them is not normally distributed
```

```

ret$final.test<-"Wilcoxon signed rank"
ret$p.value<-wilcox.test(t1,t2,paired = T)$p.value
}else{
ret$final.test<-"Student T test for paired samples"
ret$p.value<-t.test(t1,t2,paired = T)$p.value
}
return(ret)
}
test.numeric.paired.1<-function(tx){ #the same idea, but for when I supply only one group of
values
ret<-list()
ret$na_vals<-is.na(tx)
tx<-tx[!ret$na_vals]
ret$shapiro.p<-shapiro.test(tx)$p.value
if(ret$shapiro.p<0.05){
ret$final.test<-"Wilcoxon signed rank"
ret$p.value<-wilcox.test(tx)$p.value
}else{
ret$final.test<-"Student T test for one sample"
ret$p.value<-t.test(tx)$p.value
}
return(ret)
}
contingency.table.test<-function(t){
if(nrow(t)==2 & ncol(t)==2){
f<-fisher.test(t)
bigtotal<-sum(t)
can_use_chisq<-
(sum(t[1,])*sum(t[,1])/bigtotal>=5) &
(sum(t[1,])*sum(t[,2])/bigtotal>=5) &

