# already_diff should be true for WAB and NIHSS, because they are already differentials
#             false for mRS and BI, because then I will manually compute diff 3-2 4-2
table_them_all<-function(dfl,already_diff){
  ret<-data.frame(
    visit=as.character(),
    sub=as.character(),
    crb=as.character(),
    plc=as.character(),
    diff_between_grps=as.character()
  )
  names(dfl)<-c("RDMNUM","is_crb","visit","value")
  ret[1:15,2]<-c("Number of valid data points N","Mean+SD of group","Median of group","p value
(differential)","Statistical test")
  for(visi in 2:4){
    ret[(visi-2)*5+1,1]<-visi
    vc<-dfl[dfl$is_crb&dfl$visit==visi,4]
    vp<-dfl[(!dfl$is_crb)&dfl$visit==visi,4]
    vc<-vc[!is.na(vc)]
    vp<-vp[!is.na(vp)]
    ret[(visi-2)*5+1,3]<-length(vc)
    ret[(visi-2)*5+1,4]<-length(vp)
    ret[(visi-2)*5+2,3]<-descr.numeric.meansd(vc)
    ret[(visi-2)*5+2,4]<-descr.numeric.meansd(vp)
    ret[(visi-2)*5+3,3]<-descr.numeric.median(vc)
    ret[(visi-2)*5+3,4]<-descr.numeric.median(vp)
    if(already_diff)
    {
      tvc<-test.numeric.paired.1(vc)
      tvp<-test.numeric.paired.1(vp)
      ret[(visi-2)*5+4,3]<-beautiful.p.value(tvc$p.value)
      ret[(visi-2)*5+4,4]<-beautiful.p.value(tvp$p.value)
      ret[(visi-2)*5+5,3]<-tvc$final.test
      ret[(visi-2)*5+5,4]<-tvp$final.test
    }
  }else if(visi!=2){
    vc<-dfl[dfl$is_crb&dfl$visit==visi,4]-dfl[dfl$is_crb&dfl$visit==2,4]
    vp<-dfl[(!dfl$is_crb)&dfl$visit==visi,4]-dfl[(!dfl$is_crb)&dfl$visit==2,4]
    vc<-vc[!is.na(vc)]
    vp<-vp[!is.na(vp)]
    tvc<-test.numeric.paired.1(vc)
    tvp<-test.numeric.paired.1(vp)
  }
```

```

    ret[(visi-2)*5+4,3]<-beautiful.p.value(tvc$p.value)
    ret[(visi-2)*5+4,4]<-beautiful.p.value(tvp$p.value)
    ret[(visi-2)*5+5,3]<-tvc$final.test
    ret[(visi-2)*5+5,4]<-tvp$final.test
  }
  tv<-test.numeric.unpaired(vc,vp)
  ret[(visi-2)*5+4,5]<-beautiful.p.value(tv$p.value)
  ret[(visi-2)*5+5,5]<-(tv$final.test)
}
for(i in 1:nrow(ret))
  for(j in 1:ncol(ret))
    if(is.na(ret[i,j]))ret[i,j]<-""
return(ret)
}

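### The between-arm test of WAB change is valid but leaves out baseline as a covariate, and no between-arm difference or confidence interval is planned

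*SAP*

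**What the plan says.** The SAP defines the outcome under Primary objectives: "The primary outcome measure is the change in Western Aphasia Battery score from baseline to each follow-up time point (30, 60, and 90 days".

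Under Exploratory statistics, the change at each visit is tested between arms in one of two ways. If the changes pass Shapiro-Wilk, "we will compare the differentials between groups using Student T test for unpaired samples and equal or unequal variances". If not, "for each visit, we will compare the differentials between groups using a Wilcoxon rank-sum test". Neither branch has a baseline term, and none appears under Primary endpoint, under Statistical analysis or in the R code.

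The R function that builds the efficacy tables (table_them_all) writes two entries per visit in the between-group column: the p-value ("ret[(visi-2)*5+4,5]<-beautiful.p.value(tv$p.value") and the test name ("ret[(visi-2)*5+5,5]<-(tv$final.test"). The helper that runs the test keeps only the p-value, for example "ret$p.value<-wilcox.test(t1,t2,paired = F)$p.value". For each arm the same function does tabulate N, mean±SD and median with quartiles.

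Baseline AQ and NIHSS are measured at Visit 1. They are subtracted to form the changes, described, plotted, and tested under Comparability between study groups, which lists "WAB scores (and their specific subscales) and NIHSS scores". The Confirmatory statistics section says that none are planned.

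**The concern.** There are two separate gaps.

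The first is precision. Subtracting baseline fixes the slope of follow-up on baseline at 1. The score is bounded ("Aphasia Quotient (0-100" per cent under Coding systems utilized), so a patient who starts at 80 can gain at most 20, and the change can still depend on baseline. A covariate lets the data set the slope and removes the noise from chance imbalance. The SAP tests for baseline imbalance but plans no adjustment if it finds one.

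The second is reporting. In an exploratory trial the size of the difference and its uncertainty are the useful result. The planned efficacy tables print neither. The adverse-event table, by contrast, prints an odds ratio beside its p-value.

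**Working it through.** **Inputs from the SAP.** Alpha 0.05, power 0.80, d = 0.5, 1:1 allocation, Wilcoxon-Mann-Whitney test, 53 per group, 60 per arm recruited (Sample size sections); two-tailed p-values (Statistical analysis).

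**Assumptions, not in the SAP.** The baseline/follow-up correlation ρ; k = follow-up SD / baseline SD; d read in change-score SD units; normal data.

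**The SAP's own figure.** Noncentral t power with n multiplied by 3/π (the rank-sum efficiency for normal data) gives 53 per group at one-sided 0.05. Two-sided, it gives 67. The sample-size text does not state sidedness. That mismatch is a separate matter; here it explains why the starting power is below 80%.

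**Planned tests, two-sided 0.05, d = 0.5.** Noncentrality is d√(n/2), with n replaced by 3n/π for the rank-sum test.
- t test: 77.5% at 60 per arm, 72.2% at 53; 64 per arm needed for 80%.
- Rank-sum: 75.6% at 60 per arm, 70.2% at 53; 67 per arm needed for 80%.

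**Effect of adjustment.** In units of the baseline variance, Var(change) = 1 + k² − 2ρk and Var(ANCOVA residual) = k²(1 − ρ²). With k = 1 their ratio is (1 − ρ²)/(2 − 2ρ) = (1 + ρ)/2. The effective standardised difference is 0.5/√ratio.

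| ρ (k = 1) | Variance ratio | Effective d | Power, 60 per arm | Power, 53 per arm | n per arm for 80% |
|---|---|---|---|---|---|
| 0.3 | 0.65 | 0.620 | 92.1% | 88.6% | 42 |
| 0.5 | 0.75 | 0.577 | 88.0% | 83.8% | 49 |
| 0.7 | 0.85 | 0.542 | 83.8% | 79.0% | 55 |
| 0.8 | 0.90 | 0.527 | 81.7% | 76.7% | 58 |
| 0.9 | 0.95 | 0.513 | 79.6% | 74.4% | 61 |

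A simulation of 8,000 trials per setting at 60 per arm gave ANCOVA power of 0.87, 0.83 and 0.80 at ρ = 0.5, 0.7 and 0.9, with the t test at 0.77-0.78 and the rank-sum test at 0.74-0.76.

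**Unequal SDs.**
- k = 1.2, ρ = 0.8: the slope is 0.8 × 1.2 = 0.96. The ratio is (1.44 × 0.36)/(1 + 1.44 − 1.92) = 0.518/0.520 = 0.997. Power is about 77.7%, essentially no gain.
- k = 0.7, ρ = 0.7 (follow-up compressed, as by a ceiling): (0.49 × 0.51)/(1 + 0.49 − 0.98) = 0.250/0.510 = 0.49, a much larger gain.

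**Chance imbalance.** With 60 per arm the baseline difference has standard error √(2/60) = 0.18 SD, so differences up to about 1.96 × 0.18 ≈ 0.36 SD are ordinary.

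**The case against.** Several stronger readings are tempting, and the SAP does not support them.

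- **That the test is biased or invalid.** It is not. An unadjusted comparison of change is unbiased under randomisation, and change is the prespecified outcome. Chance imbalance costs precision only.
- **That baseline is used only for comparability p-values.** It also forms every change score and is described and plotted. What is missing is its use as a covariate.
- **That the tables carry no information on effect size.** A reader can derive a crude mean difference and an approximate interval from the arm-level N, mean and SD. But the SAP plans no between-arm difference or interval, and nothing printed gives the location shift and interval that match the rank-sum test.
- **That adjustment restores 80% power.** That depends on ρ and k. The extra patients are a margin for withdrawals and violations, so 60 evaluable per arm is optimistic. At 53 per arm ANCOVA stays below 80% for ρ of 0.7 and above.
- **That the gain runs from 75.6% to the ANCOVA figures.** These calculations assume normal data, for which the SAP would normally choose the t test, so 77.5% is the like-for-like start. If the data are clearly non-normal, the ANCOVA figures hold only approximately.
- **That a rank-sum sensitivity analysis guards against a non-linear baseline relation.** An unadjusted rank test does not examine that relation.

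After these corrections, the missing between-arm estimate stands whatever ρ is, and the missing covariate stands as an efficiency loss of uncertain size.

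**Conclusion.** The point holds as an improvement worth making, not as an error of validity. That the between-group column contains no difference or interval is certain from the code.

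The precision gain is conditional. With equal SDs, d in change-score units and no losses, adjustment adds about 2 points of power over the t test at ρ = 0.9 (79.6% against 77.5%) and about 15 at ρ = 0.3 (92.1% against 77.5%). At 53 per arm it adds about 2 to 16 points (74.4% to 88.6% against 72.2%). The gain can be near zero when the slope is close to 1, and larger than the table shows when follow-up scores are compressed. In large samples ANCOVA is no less efficient than the change-score comparison, so the choice carries little risk.

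**What to change.** Before unblinding:

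1. Make the primary between-arm analysis an ANCOVA of AQ change at each visit, with arm and baseline AQ as terms. Do the same for NIHSS with baseline NIHSS.
2. Put the adjusted mean difference and its 95% CI in the between-group column, beside the p-value.
3. Keep the rank-sum test as a sensitivity analysis for non-normality, with a Hodges-Lehmann shift and CI (conf.int = TRUE in wilcox.test).
4. State in advance that if the 0-100 bound makes the baseline relation non-linear, robust standard errors or a flexible baseline term will be used.

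The cost is SAP wording and a few lines of R. Baseline has to be passed to the table function, which now receives only patient, arm, visit and value. No new data are needed. The price is a linear-model assumption. The Source code section says the code should ideally not change after unblinding, so this should be settled first.

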## Statistical analysis

For comparing numeric values of paired samples, differential values for each pair of values will be computed. Then, the distribution of those differentials will be compared with the normal distribution, using the Shapiro-Wilk test. If the differentials are normally distributed, we will use a one-sample Student T test (equivalent with the Student T test for paired samples) with null hypothesis  $\mu=0$ . If the differentials are not normally distributed, we will use a Wilcoxon signed-rank test with null hypothesis location=0.

For comparing numeric values of unpaired samples the normality of the values in each sample will be tested using Shapiro-Wilk test. If values from both samples are normally distributed, then variance equality between the samples will be assessed using the Bartlett test.

If the variances are equal, then the differences between the two samples will be assessed using a Student T test for unpaired samples and equal variances. If the variances are not equal, then a Student T test for unpaired samples and unequal variances will be used. In both cases, the null hypothesis will be that mean difference is equal to 0. If values from at least one of the samples are not normally distributed, then a Wilcoxon rank sum with null hypothesis of location difference equal to 0 will be performed.

For comparing ordinal values of paired samples, a Wilcoxon signed-rank test will be used, and for unpaired samples, a Wilcoxon rank-sum test will be used.

For comparing the difference in prevalences of variants of one dichotomous or nominal variable, among the groups of another dichotomous or nominal variable (i.e. testing the association between two dichotomous/nominal variables), the Chi test will be used or, where its assumptions would be violated (mainly due to small number of patients in any group), Fisher exact test will be used.

Where applicable, the two-tail p-value is reported. The type 1 error is assumed to be  $\alpha=0.05$ , and as such, results were considered statistically significant for  $p<0.05$ .

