## Planned tables and graphs

### Planned tables

- table1demographics.xlsx: demographics and baseline characteristics of each group; this table will also contain the results of the statistical tests done for comparability between groups
- 
- itt/3dWABAQ.xlsx: WAB Aphasia Quotient differentials at visits 2/3/4, comparisons with baseline and comparisons of differentials between groups, at each visit
- itt/4dNIHSST.xlsx: NIHSS differentials at visits 2/3/4, comparisons with baseline and comparisons of differentials between groups, at each visit
- itt/5BIT.xlsx: Barthel Index scores at visits 2/3/4, comparisons of differentials from visits 3/4 against visit 2, and comparisons of those differentials between groups, at visits 3/4
- itt/6MRS.xlsx: modified Rankin Score at visits 2/3/4, comparisons of differentials from visits 3/4 against visit 2, and comparisons of those differentials between groups, at visits 3/4
- pp/3dWABAQ.xlsx: WAB Aphasia Quotient differentials at visits 2/3/4, comparisons with baseline and comparisons of differentials between groups, at each visit
- pp/4dNIHSST.xlsx: NIHSS differentials at visits 2/3/4, comparisons with baseline and comparisons of differentials between groups, at each visit

- pp/5BIT.xlsx: Barthel Index scores at visits 2/3/4, comparisons of differentials from visits 3/4 against visit 2, and comparisons of those differentials between groups, at visits 3/4
- pp/6MRS.xlsx: modified Rankin Score at visits 2/3/4, comparisons of differentials from visits 3/4 against visit 2, and comparisons of those differentials between groups, at visits 3/4
- AE\_table.xlsx: counting of total AEs, SAEs and specific AE categories, as well as statistical tests between groups.

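### At Days 60 and 90 the only coded between-arm mRS test is of change since Visit 2, where a death before Day 30 scores 0 or is deleted

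*SAP*

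**What the plan says.** Coding systems utilized defines the mRS as "total score (0-6 where 0=no symptom and 6=dead", so a higher score is worse. It adds that for BI and mRS "only scores at visits 2, 3, and 4 (30, 60 and 90 days after baseline, respectively) are available, with no value at baseline". BI runs from 0 to 100, with no value named for death.

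With no baseline score, the plan measures change from Visit 2 (Day 30): "For BI and mRS scores, differences from visit 2 to visit 3 and 4 respectively will be assessed in the same way", with unpaired tests between groups. Planned tables repeats this for the ITT and PP files: "comparisons of differentials from visits 3/4 against visit 2, and comparisons of those differentials between groups, at visits 3/4".

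Secondary endpoints, Efficacy also lists a between-arm comparison of the mRS and BI scores themselves at each of Days 30, 60 and 90, besides the comparisons with Visit 2.

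In the R function `table_them_all`, the mRS and BI vectors for Visits 3 and 4 are replaced by differences, "vc<-dfl[dfl$is_crb&dfl$visit==visi,4]-dfl[dfl$is_crb&dfl$visit==2,4", before the unpaired test is called, "tv<-test.numeric.unpaired(vc,vp".

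Missing data handling assumes values are missing completely at random, avoids imputation, and uses pairwise deletion in ITT. No section says how a death enters a change score.

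**The concern.** A change score that starts at Day 30 cannot register a death before Day 30. Treatment starts after a baseline visit 3–5 days post-stroke, and the first cycle covers study days 1–14. Deaths before Visit 2 can therefore occur on or soon after treatment.

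At Days 60 and 90, the ITT table would give a between-arm p-value in which such a death either equals stability or is absent. The p-value would carry no note saying so. A death after Visit 2 does count as worsening, but by an amount that depends on how disabled the patient was at Day 30. The arms could therefore differ in deaths without the tabled test at Days 60 and 90 reflecting it.

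**Working it through.** **1. What the code tests, visit by visit (mRS, `already_diff = F`).**

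| Visit | Vectors passed to the unpaired test | Early death |
|---|---|---|
| 2 (Day 30) | raw scores | 6, worst rank, if entered |
| 3 (Day 60) | Visit 3 − Visit 2 | 0, or deleted |
| 4 (Day 90) | Visit 4 − Visit 2 | 0, or deleted |

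The raw mean and median per arm are printed at every visit before the vectors are overwritten. Only the test changes. The raw between-arm tests listed under Secondary endpoints for Days 60 and 90 are not run, and Planned tables does not list them.

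**2. Arithmetic on the SAP's own coding.** Change = mRS at the visit − mRS at Visit 2. Ranks are among these seven example patients, 1 = best:

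| Patient | Change | Rank |
|---|---|---|
| 3 → 2 | −1 | 1 |
| 3 → 3, stable | 0 | 2.5 |
| dead by Day 30, 6 → 6 | 0 | 2.5 |
| 2 → 3 | +1 | 4.5 |
| death after Visit 2 from mRS 5 | +1 | 4.5 |
| 1 → 3 | +2 | 6.5 |
| death after Visit 2 from mRS 4 | +2 | 6.5 |

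Early death ties with no change and ranks better than a one-point worsening. A later death scores 6 minus the Visit 2 mRS, which can be as little as +1.

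**3. If 6 is entered at Visit 2 but later cells are blank.** The difference is missing and pairwise deletion drops the patient from the change comparison.

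**4. BI.** With no stated value for death, the BI difference is missing and the patient drops out. Absence caused by death cannot be presumed missing completely at random.

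**5. Size (illustration).** The SAP gives 60 per arm and two-sided α = 0.05. The rest is assumed: survivors alike in both arms, Visit 2 mRS uniform on 0–5, change −1/0/+1 in 40/50/10%, scores kept within 0–5, and 6 carried forward for early deaths.

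Expected values:
- Survivors' mean change = −0.40 + 0.10 + 0.40/6 − 0.10/6 = −0.25 (the last two terms come from the limits at 0 and 5).
- Survivors' mean at Visit 2 = 2.5, so at Visit 4 = 2.5 − 0.25 = 2.25.
- 6 versus 2 early deaths is a gap of 4 in 60. Raw Day 90 difference = (4/60) × (6 − 2.25) = 0.25. Difference in change = (4/60) × (0 + 0.25) = 0.017.

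The simulations gave about 0.24 and 0.02.

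Rejection rates over 3,000–4,000 simulated trials per run:

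| Early deaths | Raw Visit 2 | Raw Visit 4 | Change | Change, deaths worst |
|---|---|---|---|---|
| 10 vs 2 | 20–22% | about 21% | about 6% | 24–26% |
| 6 vs 2 | about 7% | about 7% | about 5–6% | about 7–8% |

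If survivors mostly worsen (10/50/40%) with 10 versus 2 deaths, the mean change differs by about −0.03, slightly favouring the arm with more deaths. Most of that test's roughly 6% rejections then favour that arm.

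**The case against.** The strongest defence is that early deaths are already captured elsewhere.

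- **The Day 30 test.** It uses raw mRS and ranks an early death worst when 6 is entered. In the 10 versus 2 illustration it rejects in 20–22% of trials. This stands. A reader might infer that the plan hides early deaths from the mRS analysis altogether, but the code does not support that. The gap is confined to the ITT tests at Days 60 and 90. PP is largely unaffected, because it requires complete WAB and NIHSS at Visits 2, 3 and 4.
- **Raw scores at Days 60 and 90.** The endpoint section already promises these comparisons, and the table and boxplots show the raw scores. This stands for the text but not for the code, which never runs those tests. They need to be run, not newly invented.
- **What a change score is for.** A change from Day 30 describes Days 30–90 and was not meant to show first-month harm. That is fair, but it does not justify tabling a dead patient as stable in a between-arm ITT test.
- **Late deaths.** A reader might infer that a death is neutral, absent or the worst value according to its date alone. That goes too far: a death from mRS 5 scores only +1, so the score also depends on the Visit 2 mRS.
- **Consequence.** mRS and BI are secondary, no confirmatory analysis is planned, and SAE incidence is compared separately. This stands and limits the severity.

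**Conclusion.** The point holds for the ITT between-arm tests of mRS change at Days 60 and 90, and in a related form for BI change. An early death scores 0 if 6 is carried forward and is deleted if it is not. The SAP does not say which, and under neither convention does it count as a bad outcome. Because the code omits the promised raw tests at those visits, no other between-arm mRS test there makes up for this.

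The size rests on assumed death counts and mRS distributions; the SAP gives none. With 10 versus 2 early deaths, rejection is about 6% on change against about 21% on raw Visit 4 mRS. With 6 versus 2, a reader might infer that a real signal would be missed, but no test has useful power there. The effect in that case is on the estimate, about 0.02 against 0.24 points.

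Severity is low to moderate. It should be corrected before unblinding.

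**What to change.** 1. In `table_them_all`, run the raw between-arm mRS rank-sum test at Visits 3 and 4, as Secondary endpoints, Efficacy already states. List it in Planned tables. State that 6 is carried to every visit after death.
2. In Exploratory statistics, state that in the between-arm tests of mRS and BI change every patient dead by that visit takes the worst rank, whenever the death occurred. In code, assign a value outside the possible range on the bad side (above +6 for mRS change, below −100 for BI change).
3. Call the rank-sum test directly for these comparisons instead of choosing by the Shapiro-Wilk result. For ordinal data the SAP already says that "for unpaired samples, a Wilcoxon rank-sum test will be used".
4. Pass death status into `table_them_all`. It now receives only the patient number, arm, visit and one score, so the BI call cannot see an mRS of 6.
5. Print deaths per arm beside each table. Label any mean or median change as survivors only; the table now prints raw means and medians beside a p-value for change.

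The cost is a few sentences and a modest code edit, using the mRS death code. The downside is that the change test becomes a composite with death, while its summaries describe survivors only. Early deaths also count both there and in the Day 30 test. The within-arm paired tests are not altered by this and need their own statement on how deaths are handled.
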